Data collection for Aims 1 and 2. This RCT focuses on comparing NDPP outcomes between participants who receive Pre-NDPP vs. direct enrollment into the NDPP. The assessment schedule is shown in Table 1 below. Demographic characteristics will be extracted from EHR databases and verified as needed during the first study visit, including age, gender, race/ethnicity, preferred language, income (above/below 133% of federal poverty level), and education (highest level completed). Body weight will be measured on a high-capacity medical-quality scale at study visits and NDPP sessions. We will also provide study participants with a commercial-grade scale for in-home use (e.g., Inevifit's Premium Bathroom Scale I-BS002; https://www.inevifit.com/product/inevifit-premium-bathroom-scale-w-led-display-silver/) so that they can send us a picture of their weight via text message or email when not meeting in-person. The primary outcome is percent weight change from baseline to 12-months by ITT analysis (without regard to whether participants declined NDPP or had early dropout). We will also calculate percent weight change from the first to last NDPP sessions attended (i.e., last observation carried forward), per CDC guidelines.³⁷ CMS standards for NDPP reimbursement also emphasize achieving ≥5% weight loss at any point in the program, ¹⁰ assessed as a

dichotomous outcome. Attendance in the NDPP will be measured as ≥1 session attended, total number of NDPP sessions attended (including make-up sessions), and duration of participation in the yearlong program. We will also record how many sessions were attended remotely vs. in-person. Rates of completing between-session support calls will also be assessed as an additional indicator of engagement and treatment dose. Per the CDC's NDPP curriculum, participants will self-report weekly minutes of moderate to vigorous physical activity since the last session.³ Baseline BMI will also be assessed at the initial study visit as kg/m². If the initial study visit is held remotely (i.e., due to restrictions to meeting in-person per COVID-19), we will collect BMI by confirming height from a participant's medical record, and mailing a scale to participants for them to send us a picture of their weight within 1-2 weeks.

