Retention. We aim to have 400 randomized participants across arms attending ≥1 NDPP session. We established initial retention rates during our 2013-2017 NDPP delivery and Pre-NDPP pilot as described above and in Preliminary Data (e.g., 83% [n=75] of participants attended the NDPP after completing a pre-session). We expect similar rates of early retention following the initial assessment in this study. Note dropout does not impede our ability to test main effects of Pre-NDPP on NDPP attendance and weight loss as: 1) NDPP engagement is a main outcome of interest; 2) The primary outcome of percent weight loss from baseline to 12 months will be assessed by intent-to-treat (ITT) analysis. Imputation methods for missingness will be used as appropriate (see Analysis Plan). For generalizability, we will deliver NDPP with only customary retention methods: offering classes at clinics where participants receive their primary care (with an option to join classes remotely, as allowable by the CDC since 2018²³), facilitating transportation as needed (e.g., providing free parking and information about insurance-provided transportation benefits), offering make-up sessions as needed, and updating participant contact information often. To reduce both participant and study staff burden, make up sessions will be offered primarily as a pre-recorded audio and/or video of the Lifestyle Coach talking through the session content (without other participants present). Coaches will seek to follow up briefly (e.g., 10-15 minutes) with participants via phone to ensure comprehension and address remaining questions. To accommodate additional data collection required of participants in both arms of the trial (above and beyond routine care in the NDPP), we will provide compensation of \$25 for completing each of two 30-minute research assessments at the time of initial recruitment and immediately prior to attending the NDPP. We will also provide an additional \$25 for all participants to complete a final study visit for weight measurement at 12 months (which may be collected via an in-home, study-provided scale as needed).

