General quantitative approaches. Differences in characteristics between study groups will be assessed using chi-square and t-tests to examine potential sampling bias. Percent weight change is the primary outcome, which has a well-documented association with T2D incidence.^{2,20} ITT analyses will include all randomized participants regardless of NDPP participation, including those lost to follow up. Weight loss data for women who become pregnant during the study will be excluded from analyses. Patient-level covariates will be screened in bivariate analyses and included in multivariate analysis if related to the outcome at p<.2, differ between treatment arms, or associated with dropout. Covariates and potential moderators will include age, gender, race/ethnicity, primary language, comorbidities, and other demographic and clinical variables. Although primary analyses examine a single outcome per patient (e.g., percent weight loss), for longitudinal analyses (e.g., perceived risk) we will determine whether missingness patterns are ignorable or nonignorable. 51-54 If so, we will employ likelihood-based methods that use all available data, adjusting for covariates associated with missingness. If missingness is non-ignorable we will use pattern mixture models.⁵⁵ If normality assumptions are not met, we will use transformations to normalize distributions, ordinal or Poisson regression where appropriate, and/or the appropriate link function and distribution (e.g., logit link, gamma distribution). We will use general (generalized) linear mixed models to incorporate data structures that may be both hierarchical (patients within groups) and longitudinal (repeated observations over time). 56,57 Hypothesis tests will be two-sided with α=.05 or p values reported. Goodness of fit statistics and model fitting diagnostics will be used to assess for influential points, outliers, overdispersion, and heteroscedasticity and to evaluate alternative model specifications.⁵⁷ SAS version 9.4 (SAS Institute Inc., Cary, NC) will be used for analyses.

Aim 1: To evaluate clinical effectiveness of the Pre-NDPP intervention.

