Hypothesis 1.1. Pre-NDPP participants will experience greater weight loss than those directly enrolled into NDPP. The primary outcome for this analysis will be percent weight change among all randomized participants. As study participation includes groups of individuals in the same study arm, the data structure will be hierarchical, with patients nested within groups. Statistical models are shown in hierarchical notation below.

Likelihood of achieving ≥5% weight loss in the NDPP will also be evaluated (using generalized linear mixed models with logit link), as well as percent weight change from first to last NDPP sessions attended.

Level 1 model. Individual outcomes will be modeled as a function of patient characteristics (fixed effects), such as sociodemographic variables, baseline BMI, and comorbid conditions: $Y_{ij} = \beta_{0j} + \beta_{1j} X_{1ij} + \beta_{2j} X_{2ij} + ... + \beta_{pj} X_{pij}$ Level 2 model. Group level models specify relationships between group-level predictors and coefficients in the Level 1 model. The intervention effect is included as 0 if control, 1 if intervention: $\beta_{0j} = \gamma_{00} + \gamma_{01}$ (intervention)+ u_{0j} . Thus, for a standardized model, γ_{00} is adjusted mean weight loss for patients in the standard condition (i.e., no pre-session intervention), γ_{01} represents the average increment (decrement) from the mean for groups with intervention patients, and u_{0j} is a group level random effect that reflects between-group variance and is the difference between group means and the predicted mean based on the model, and $u_{0j} \sim N(0,\tau_{00})$. Thus, Hypothesis 1.1 can be tested as H_0 : γ_{01} =0 vs H_1 : γ_{01} ≠0.

Hypothesis 1.2. Pre-NDPP participants will have greater engagement in the NDPP than those who are directly enrolled into the program. The outcome variables, number of sessions attended and days of participation, will be analyzed using similar approaches. If the distribution of outcomes is non-normal we will use generalized linear mixed models with the appropriate distribution and link function, as described above. We will also examine the dichotomous outcome of ≥1 NDPP session attended using multilevel logistic regression (generalized linear mixed model with logit link and random effect for group).

Aim 2: To examine mediators and moderators of Pre-NDPP outcomes.

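### Does the plan need changing because it names no missing-data method for the 12-month weight outcome?

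*Combined protocol and SAP*

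**What the plan says.** Section IV.A defines the primary outcome as percent weight change from baseline to 12 months, by intention to treat (ITT), whether or not a participant took up or stayed in the classes. Carry-forward appears there only for a second measure: "percent weight change from the first to last NDPP sessions attended (i.e., last observation carried forward".

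Section IV.C, Retention, states: "Note dropout does not impede our ability to test main effects of Pre-NDPP on NDPP attendance and weight loss". It gives two numbered reasons: engagement is itself an outcome, and the weight outcome is analysed by ITT. A separate sentence follows: "Imputation methods for missingness will be used as appropriate (see Analysis Plan".

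Section IV.F, General quantitative approaches, sets the population: "ITT analyses will include all randomized participants regardless of NDPP participation, including those lost to follow up". The next sentence reads: "Weight loss data for women who become pregnant during the study will be excluded from analyses". Covariates enter the model if they predict the outcome at p<.2, differ between arms, or are associated with dropout. Then comes "Although primary analyses examine a single outcome per patient (e.g., percent weight loss), for longitudinal analyses (e.g., perceived risk) we will determine" whether missingness is ignorable. For the ignorable case, "we will employ likelihood-based methods that use all available data, adjusting for covariates associated with missingness"; otherwise pattern mixture models are used.

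Hypothesis 1.1 repeats the population ("The primary outcome for this analysis will be percent weight change among all randomized participants") and gives a two-level model with one value per patient. It does not mention a missing value.

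**The concern.** The Retention text points to an imputation method that a reader cannot find in section IV.F. The likelihood and pattern-mixture methods there are worded for longitudinal measures such as perceived risk. The carry-forward rule belongs to the secondary weight measure.

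Two smaller points add to the impression of a hole:

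- **Baseline weight.** Recruitment lists randomization (step 2) before the anthropometric assessment (step 3), and a remotely collected weight may arrive 1–2 weeks later. No rule covers a weight that never arrives.
- **Pregnancy.** All randomized participants are included, yet the weight data of women who become pregnant are excluded. The text does not say whether these women leave the ITT set or have a missing outcome.

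At stake is the freedom to choose a method after seeing the results. The Hypothesis 1.1 estimate also feeds the payer return-on-investment calculation.

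**Working it through.** **1. The plan's own figures.** Table 2 uses effective sample size = g·m / (1 + (m−1)·ICC) per arm, with g classes of m patients. For 10 classes of 20 at ICC 1%: 200/1.19 = 168.1 (stated 168). Power at effect size 0.31: 0.31 × √(168.1/2) − 1.96 = 0.88, which gives 81.1% (stated 81%). The other five rows also reproduce. The inflation for attrition is 400/(1 − 0.20) = 500, as stated. No sample-size figure is wrong.

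**2. What is fixed and what is open.**

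| Element | Status |
|---|---|
| Outcome and time point | Fixed (IV.A) |
| Population | Fixed: all randomized (IV.F) |
| Model, test, level | Fixed (Hypothesis 1.1; two-sided .05) |
| Collection of the 12-month weight | Fixed: scheduled for everyone randomized, $25, home scale allowed (Table 1; Retention) |
| Adjustment for dropout | Partly fixed: covariates associated with dropout enter the model; this sentence is not limited to longitudinal analyses |
| Whether to impute | Committed to, as appropriate (Retention) |
| Which imputation method | Open |

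**3. Sensitivity even if missing outcomes were simply left out.** Assume 10 classes of 25 per arm (50 recruits and two classes per quarter over 2.5 years, one class per arm) and the pilot ICC of 1.44%. The detectable effect at 80% power is (1.960 + 0.842) × √(2/ESS), where ESS is the effective sample size per arm.

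| Missing (assumed) | ESS per arm | Detectable effect |
|---|---|---|
| 0% | 185.8 | 0.291 |
| 20% | 157.0 | 0.316 |
| 30% | 141.4 | 0.333 |
| 40% | 124.8 | 0.355 |

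Up to 30% missing, this stays inside the plan's stated 0.28–0.35.

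**4. How far the method moves the estimate.** The plan gives no SD. From the pilot, 1.9/0.36 = 5.28, so 0.31 SD = 1.64 points. With the same missing share m in both arms, treating missing people like the observed people of their arm gives 1.64. Setting their change to zero gives (1 − m) × 1.64, which is 1.57 at 4%, 1.31 at 20% and 1.18 at 28%. These shares come from Table 2 totals (480, 400, 360) against 500. They are sample-size scenarios, not counts of missing weights. The test hardly moves: zero-filling shrinks the difference by (1 − m) and the SD by about √(1 − m), while the number analysed rises by 1/(1 − m), so the effects nearly cancel. The computed ratio of test statistics was 0.97–1.00.

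**5. Simulation.** The set-up was 500 people, 10 classes of 25 per arm, 20% never attending, pilot attendance of 35.0% and 49.3%, 0.31 points per session, ICC 1.44%, and a test on class means with 18 df. Assumed inputs were weight capture rising from .68 at no sessions to .97 at 25 (21–24% missing), a correlation of 0.7 between last-session and 12-month deviations, and an added effect to reach 1.64.

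| Method | Mean estimate (true 1.64) | Power | Rejection under no effect |
|---|---|---|---|
| Baseline carried forward | 1.42 | 77% | 5.0% |
| Last session carried forward | 1.58 | 82% | 5.6% |
| Multiple imputation without attendance | 1.70 | 68% | 3.6% |
| Multiple imputation with attendance and session weight | 1.63 | 71% | 4.4% |

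A separate run of the same set-up (3,000 trials, attendance spread assumed) used observed outcomes only and gave 1.71 with 76% power. With 4% missing at random and a true difference of 0.88, the four methods gave 0.85–0.88.

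**6. The two smaller points.** Pregnancy: P(age < 45) = Φ((45 − 48.4)/12.7) = 0.394, assuming a normal shape. Then 500 × 0.78 × 0.394 = 154 women, and an assumed 1–5% pregnancy rate affects about 2–8 people. Baseline: BMI is an eligibility criterion (IV.B), coaches pre-screen from the medical record (IV.C), and section IV.D describes the first visit as covering both eligibility and baseline. A weight that never arrives is possible but should be uncommon.

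**The case for a change.** The best case for a change runs as follows. With one value per patient, a likelihood model gains nothing from someone whose value is missing, so the methods in IV.F cannot be borrowed as they stand to deliver an analysis of everyone randomized. Adjusting for covariates linked to dropout supplies no missing value either. In the simulation, the four methods disagreed on p<.05 in 18% of trials. Under no effect, at least one of them rejected in 7.3%. An unnamed method therefore leaves some room for choice, and naming one would cost only wording.

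The reading of the text stands: IV.F does not name the method. The rest carries less weight.

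- The 18% counts any disagreement among four methods, including an imputation that ignores attendance. Baseline carried forward and the fuller imputation disagreed in 10%, and baseline carried forward and observed outcomes alone in 7%.
- The 7.3% needs about a fifth of weights missing and an analyst who picks the most favourable of four results.
- The Retention statement on dropout rests on its two numbered reasons. Leaving classes is not the same as having no 12-month weight.
- A rule for pregnancy does exist. Only its fit with the ITT set is unstated.
- The most detailed candidate, multiple imputation with attendance and session weight, was nearly unbiased but had 71% power against 77–82% for the single-value methods. That is a matter of judgement, not a clear improvement.

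**Conclusion.** No change to the plan follows. This is a gap of detail that a competent analyst fills within the commitments already made: analyse everyone randomized, impute, and adjust for what predicts dropout. Nothing in the plan prescribes a complete-case primary analysis, no stated number is wrong, and following the plan with any of the four methods tested kept type I error at 3.6–5.6%. The pregnancy and baseline points are matters of wording that concern few people.

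At about a fifth of weights missing, the choice of method moves the mean estimate between 1.42 and 1.70 for a true 1.64. At 4% missing it hardly matters. These figures rest on an SD back-calculated from the pilot, an assumed capture curve and correlation, and the same capture rule in both arms. The plan gives no missing rate for 12-month weights, so the actual effect is unknown. A high or clearly unequal missing rate between arms would make the choice matter more, but nothing in the documents predicts one.

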We will assess potential mediators of perceived risk and self-efficacy, key constructs of the Health Belief Model, ²⁶ as well as readiness for weight loss as an indicator of motivation. Perceived risk for developing diabetes will be assessed with the Risk Perception Survey for Developing Diabetes, a 53-item Likert scale measure with four subscale scores on Comparative Disease Risk, Environmental Risk, Personal Control, and Optimistic Bias. ^{41,42} Self-efficacy for weight control will be measured with the Weight Efficacy Lifestyle Questionnaire, a 20-item measure of confidence (on a 10-point scale) managing five situational factors related to weight management behavior: negative emotions, availability, social pressure, physical discomfort, and positive activities. ⁴³ We will use validated Spanish-language versions of both measures. ^{42,44} Weight loss readiness will be assessed with the Stages of Change in Overweight and Obese People (S-Weight), a 5-item survey developed concurrently in English and Spanish by expert consensus. ^{45,46} Mediators will be measured during an initial assessment at the time of enrollment and 1-2 weeks prior to the first NDPP session (i.e., about one week after pre-sessions are completed for the Pre-NDPP arm, and shortly before NDPP classes begin for both arms). This will determine whether Pre-NDPP results in increased perceived risk, self-efficacy, and readiness compared to the usual care NDPP, and whether changes in these variables mediate outcomes.

Data collection for Aim 3. RE-AIM is a planning and evaluation framework for implementation research that will guide our evaluation of Pre-NDPP delivery and effectiveness.⁸ RE-AIM constructs will be assessed through a combination of recruitment data, intervention outcomes, staff logs, observations, and interviews with Lifestyle Coaches, clinic personnel, and patients, as well as cost records (Table 1). [name] holds expertise in implementation research and will lead qualitative data collection with [name] (Qualitative Research Assistant; QRA), first developing semi-structured interview guides⁴⁷, surveys, and a structured observation template. Health economist [name] will lead cost-related data collection.

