Recruitment. We will identify potential participants through referrals from healthcare providers at DH, which is known to support initial enrollment in the NDPP.²¹ Providers refer through the electronic health record (EHR) per usual practice. Since 2013 over 7,000 at-risk patients were referred by providers to the DH NDPP. If needed to meet recruitment goals, we will also identify participants from a risk registry based on EHR data, which has previously identified over 10,000 NDPP-eligible patients annually. The enrollment process after initial identification will be as follows: 1) Lifestyle Coaches pre-screen via medical record review and contact referrals by phone to verify interest, eligibility, and schedule eligible individuals for an initial screening visit (held in-person or remotely as needed), 2) consenting individuals are randomized to receive Pre-NDPP or usual care NDPP (note we will use Denver Health's e-consent process for any virtually-conducted recruitment visits), and 3) complete an initial assessment (behavioral and anthropometric assessments), 4) the Pre-NDPP group completes a pre-session 1-2 weeks before NDPP classes start, 5) both groups complete a follow up behavioral

assessment 1-2 weeks before NDPP classes start (collected in-person or remotely as needed), and 6) both groups commence yearlong NDPP classes (held in-person or remotely as needed).

We will initially enroll 500 participants, with a goal of 400 randomized participants across both groups attending ≥1 NDPP session as based on statistical power estimates (see Sample Size and Power Calculations below). From previous experience, we expect approximately 50% of referred patients to express interest in participating upon initial outreach. Then after initial assessment, we expect early attrition of approximately 20% of consenting participants. We will seek to recruit 50 individuals every 3 months, for a total of 500 participants recruited over 2.5 years (i.e., 200 participants annually). From 2013-2017, we recruited 300 NDPP participants on average each year. Thus, we expect to fully meet RCT recruitment goals. Demographic characteristics of individuals in this study are expected to approximately match characteristics of all previous NDPP participants at DH: 78.0% female, 58.2% Hispanic, 19.5% NHB, 21.0% NHW, 61.4% low-income (including a majority of low-income individuals within each racial/ethnic group), and a mean age of 48.4 (SD=12.7) years.

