Hypothesis 2.1. The Pre-NDPP intervention will increase perceived risk for developing diabetes and self-efficacy and readiness for weight management. Outcomes for these analyses will be patients' perceived risk, self-efficacy, and readiness scores over time. We will use longitudinal models to determine if trajectories differ for patients in control vs. intervention groups, shown below in mixed model notation:

 $Y_{tij} = \gamma_{000} + \gamma_{010}$ (intervention) + γ_{100} (time) + γ_{110} (intervention x time) + $u_{00j} + r_{0ij} + \epsilon_{tij}$, where γ_{000} represents the initial status for control groups; γ_{010} represents the baseline difference between intervention and control groups (should be close to 0); γ_{100} is the change in scores for groups of control patients; γ_{110} is the difference in change for control vs. intervention groups. r_{tij} is a patient random effect and U_{00j} is a group random effect, independent of r_{tij} and assumed to have a bivariate normal distribution over practices; ϵ_{tij} is residual variance. Thus, the Pre-NDPP effect can be tested as H_0 : γ_{110} =0 vs H_1 : γ_{110} \neq 0.

Hypothesis 2.2. Perceived risk, self-efficacy, and readiness will mediate relationships between Pre-NDPP treatment and outcomes. Outcomes will be weight loss and session attendance, using similar approaches as described above for Hypotheses 1.1 and 1.2. We will include baseline perceived risk, self-efficacy, and readiness as covariates and change in these constructs as primary independent variables to determine if the intervention effect is partially or fully explained by these hypothesized mediators.⁵⁸

Hypothesis 2.3. Pre-NDPP effects will differ for participants with the moderator condition (e.g., Hispanic; low-income) compared to those without the moderator (non-Hispanic; higher income). The effects of moderator analyses involve inclusion of an intervention x moderator fixed effect for models that are not longitudinal (e.g., percent weight loss, number of sessions attended). For longitudinal models (e.g., self-efficacy over time) models will include a main effect for time, arm, moderator variable, time x arm, time x moderator, arm x moderator, and time x arm x moderator interaction term. The 3-way interaction term tests for differential intervention effectiveness in subgroups identified by the moderator variable.

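### Hypothesis 2.1 is tested by comparing change scores; adjusting for the baseline score would be more precise, provided baseline scores are unaffected by allocation

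*Combined protocol and SAP*

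**What the plan says.** Section IV.F, Aim 2, Hypothesis 2.1 concerns the three mediator scores: "Outcomes for these analyses will be patients' perceived risk, self-efficacy, and readiness scores over time". The model has fixed effects for intervention, time and intervention x time, random intercepts for class and patient, and a residual. The intervention coefficient "represents the baseline difference between intervention and control groups (should be close to 0"; it is nevertheless a free parameter. The tested coefficient, on the interaction, "is the difference in change for control vs. intervention groups".

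Section IV.A fixes the number of time points at two: "Mediators will be measured during an initial assessment at the time of enrollment and 1-2 weeks prior to the first NDPP session". Table 1 agrees.

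The baseline score is not a covariate for Hypothesis 2.1. It is one in the next paragraph, for the weight and attendance models of Hypothesis 2.2: "We will include baseline perceived risk, self-efficacy, and readiness as covariates and change in these constructs as primary independent variables". The covariate screening under General quantitative approaches names demographic and clinical variables, so it would not bring the baseline score into Hypothesis 2.1.

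No correlation, standard deviation, ICC or power is given for the mediator scores. Sample size and power describes mediation and moderation analyses as exploratory with power unknown.

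**The concern.** When both arms have the same expected baseline score, a free baseline arm term estimates a quantity whose expected value is already known. The chance baseline difference is then subtracted in full from the follow-up difference, when only the part that predicts follow-up should be removed. The result is a larger standard error for the same target.

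Hypothesis 2.1 is the plan's direct test of whether the pre-session moves the mechanisms it is meant to move, and section IV.E already expects limited power for mediators. Precision that can be had from data already collected is worth having.

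**Working it through.** **Plan's own figure.** There is none for Hypothesis 2.1. Table 2 concerns percent weight loss only.

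**Inputs**
- Sample size (Recruitment): "We will initially enroll 500 participants, with a goal of 400 randomized participants across both groups attending ≥1 NDPP session". With 1:1 allocation, 250 per arm.
- Classes (description of the NDPP): two new classes per quarter for 2.5 years, arms kept separate. That is 10 quarters x 2 = 20 classes, 10 per arm, and 250/10 = 25 patients per class.
- ICC: 1.44%, stated for percent weight change. Applying it to mediator scores is an assumption.
- Missing second assessments: 20%, borrowed from the expected early attrition. The documents do not say that these are the patients who miss the second survey.
- r: not stated. The plan names only a term that "is a patient random effect", with no variance. Range used: 0.3 to 0.9.
- Score variance: taken as 1 and equal at both times; it cancels in the ratios.
- Test level: "Hypothesis tests will be two-sided with α=.05 or p values reported".

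**Step 1: what the planned test is.** Let D0 and D1 be the arm differences in mean score at baseline and follow-up. With two times, complete pairs and a free baseline term, the interaction estimate is D1 - D0. Generalised least squares for the written model gives exactly the change-score variance: at r = 0.5 and 200 per arm, 2(1-r) x 2/200 = 0.0100, whether the class ICC is 0, 1.44% or 5%.

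**Step 2: complete data, no clustering.** The change-score variance is proportional to 2(1-r). The baseline-adjusted (or common-baseline) variance is proportional to 1-r². The ratio is (1+r)/2, so the loss is (1-r)/2. The planned standard error is larger by the factor 1/√(1-loss).

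**Step 3: add the class effect.** With m per class, the loss becomes (1-r)/(2 x DE), where DE = 1 + (m-1) x ICC = 1 + 24 x 0.0144 = 1.3456.

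**Step 4: missing second assessments, no clustering.** The loss is 0.8(1-r)/[(1+r) + 0.8(1-r)]. At r = 0.5 this is 0.4/1.9 = 21%.

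**Step 5: both together.** From the information matrices of the free-baseline and common-baseline models, 10 classes of 25 per arm. At r = 0.5 the variances are 0.00949 and 0.00801, a loss of about 16%.

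| r | Loss: complete, no clustering | Loss: ICC 1.44%, complete | Loss: 20% missing, no clustering | Loss: both | SE factor: first case | SE factor: both |
|---|---|---|---|---|---|---|
| 0.3 | 35% | 26% | 30% | 22% | 1.24 | 1.14 |
| 0.5 | 25% | 19% | 21% | 16% | 1.15 | 1.09 |
| 0.7 | 15% | 11% | 12% | 9% | 1.08 | 1.05 |
| 0.9 | 5% | 4% | 4% | 3% | 1.03 | 1.02 |

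**Step 6: illustration on the power scale.** Assume r = 0.5 and a 0.2 SD effect (neither is in the documents) and use the normal approximation Φ(0.2/SE - 1.96). With 250 per arm, complete data and no clustering, the variances are 0.0080 and 0.0060, and power is 61% planned against 73% adjusted. With ICC 1.44% and 20% missing it is 54% against 61%.

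**Step 7: what adjustment relies on.** With complete data and no clustering the adjusted estimate is D1 - r x D0. Suppose knowing the arm shifts reported scores by δ.
- Shift at both assessments: the change score is unbiased, because δ cancels. The adjusted estimate is off by (1-r)δ. At r = 0.5 and an assumed δ of 0.1 SD, that is 0.05 SD.
- Shift at baseline only: the change score is off by δ in full, the adjusted estimate by r x δ.

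**The case against.** The strongest objection is that equal expected baselines are not secured by the documents. A reader might take it that randomisation makes the baseline difference zero. It does so, in expectation, only for a score taken before allocation or unaffected by it. The enrolment steps under Recruitment put randomisation second and the initial assessment third. Section IV.D describes the first visit as covering eligibility and baseline, which leaves the order unclear. Lifestyle Coaches, who deliver classes in both arms, administer the surveys. If patients know their arm when they answer, and the shift persists, the planned test is the more robust one (Step 7). This stands as a condition on the fix.

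It also stands that no single percentage can be read off the documents. The loss depends on an unstated r, and the plan's own class effect and missing follow-up both reduce it. With missing second assessments the likelihood fit also uses patients with a baseline score only, so it is no longer exactly a change-score test. The formulas assume a linear model with equal variances. They may not apply to the five-item readiness measure if that is analysed as ordinal, which the plan allows.

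Two stronger readings are not supported. One is that the planned test is biased or invalid: if baseline is unaffected by allocation, it is neither. The other is that the effects in Hypotheses 2.1 and 2.2 cannot be combined because only the second conditions on baseline. With equal expected baselines, both forms of the arm effect on the mediator have the same target. In Hypothesis 2.2, the coefficient of change given baseline equals that of follow-up given baseline, since b(F-B) + cB = bF + (c-b)B. Nor does the plan propose a product of paths; it asks how much of the intervention effect the mediators explain.

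Finally, Aim 2 has no power target. That lowers the stakes but is no reason to prefer the less precise estimate.

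**Conclusion.** The point holds as one of efficiency. For any r below 1, the planned test is less precise than a baseline-adjusted one, and nothing else in the plan supplies that adjustment for Hypothesis 2.1. Over r = 0.3 to 0.9 the avoidable share of the variance runs from 35% down to 5% in the simplest case, and from about 22% down to 3% under the borrowed ICC and attrition figures. In that second case the planned standard error is about 14% down to 2% larger than it need be.

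These sizes rest on an assumed r, equal variances at the two times, a linear model, and baseline scores unaffected by allocation. The consequence is confined to an aim without a power calculation whose mediation and moderation analyses are labelled exploratory. The primary outcome, its model and its sample size are untouched.

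**What to change.** For mediator scores analysed with a linear model, specify one of these:
- regress the follow-up score on arm and the baseline score, with the class random effect; or
- to the same end, keep the longitudinal model, omit the intervention main effect so that both arms share one baseline mean, and test intervention x time.

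Bring the longitudinal models of Hypothesis 2.3 into line. Under the common-baseline form, the arm and arm x moderator terms come out; time, moderator, time x moderator, time x arm and the three-way term remain. State separately how readiness will be handled if it is analysed as ordinal.

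State in the protocol whether baseline surveys are completed before the arm is disclosed, and reconcile the enrolment steps with section IV.D. If they are not, or if this cannot be established, retain the planned change-score test alongside the adjusted one and report both.

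The cost is a few lines of model specification and one clarification of visit order, with no new data. The downside is the exposure to (1-r) of any allocation-driven shift that persists from baseline to follow-up, which is why the order needs settling first.
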